4.4 Follow-up period

Procedures will be performed according to the Follow-up Period Study Plan ([Table 3](#) and [Table 5](#)).

Subjects who complete the double-blind treatment period (Week 52) but do not continue with IP treatment will have follow-up visits at Week 56 and Week 60. Subjects who complete the second year extension will have follow-up visits at Week 108 and Week 112. Subjects who discontinue the IP before Week 52 and are not continuing on the study schedule should complete the Week 52 procedures. Subjects who discontinue the IP between Week 52 and Week 104 and are not continuing on the study schedule should complete Week 104 procedures. All other early discontinuation subjects should be followed until Week 52 or Week 104 (or for a minimum of 12 weeks after last dose of IP for subjects for whom IP was discontinued within 12 weeks prior to Week 52 or Week 104) (see [Section 3.9](#)).

5. STUDY ASSESSMENTS

The Investigator will ensure that all study assessment data are recorded in the eCRF and also ensure the accuracy, completeness, and timeliness of the data recorded and of the provision of answers to data queries according to the Clinical Study Agreement. The Investigator will sign the completed eCRFs. A copy of the completed eCRFs will be archived at the study site.

The Site Manual will include a description of specific procedures. All the assessments and laboratory tests (unless otherwise specified) will be done prior to administration of IP.

5.1 Efficacy assessments

Efficacy measurements will be made at the times indicated in the Study Plan (for assessments to be performed at Screening and treatment period, see [Table 2](#) and [Table 4](#), respectively, and for those at Follow-up, see [Table 3](#) and [Table 5](#)).

The efficacy assessments based on laboratory tests include:

- Urine protein to creatinine ratio: This consists of:
 - **24-hour UPCr**: The 24-hour UPCr will be determined on a 24-hour UPCr sample.

This will be performed twice during the screening period, Weeks 0, 12, 24, 36, 52, 64, 76, 88, and 104 and at Early Discontinuation visit.

During the screening period two samples will be required:

- Screening sample at the start of the screening process, after the ICF is signed and
- Stratification sample within 14 days prior to the expected day of randomisation. Without the results of the second (stratification) sample, subjects cannot be randomised. Turn-around time for results from central laboratory is up to 7 days.

Starting from Week 0, the 24-hour UPCR sample must always be collected before the administration of IP. The sample collected at Week 0 (Day 1) will be the baseline sample which must be provided on Day 1 prior to randomisation and administration of first dose of IP.

The collection of the 24-hour UPCR sample should start preferably in the morning of the day before the scheduled visit and end in the morning of the day of the visit. The urine collection can be done within 1 day prior to the visit if the urine sample can be kept refrigerated until the day of the visit. The sample should be kept refrigerated whenever possible. If refrigeration is not possible, subjects should select the coolest possible place to store their urine sample, eg, a cool room or use a portable cooler with ice/ice pack.

In case subject has a medical reason which would impact the validity of the assessment of proteinuria (eg, urinary tract infection, heavy menstruation), or the sample was not collected appropriately, the collection of the sample may be done/repeated as follows:

- Screening samples: As soon as possible before the next scheduled sampling is due
- Week 0: Prior to IP administration (which may require the Visit 1 to be postponed)
- Weeks 12, 24, 36, 52, 64, 76, 88, and 104: Within 2 weeks of the actual date of visit when the collection was due and if applicable, before any change in SOC or concomitant medications is made (Week 52 sample must be collected before second year extension period dosing)

The 24-hour UPCR will be used only for the primary and secondary endpoints, the PRR, aCRR, graded CRR, and graded aCRR criteria at Week 52 and Week 104, the 24-hour UPCR and CRR at Week 104 and to determine withdrawal criteria at Weeks 12, 24 and 52.

- **Spot UPCR:** Spot UPCR will be performed at all visits and will be used for the calculation of SLEDAI-2K and for the CRR and PRR classification, when evaluating time to achieve renal response modified to include OCS tapering requirement as well as for the CRR and PRR

classification for flare assessments. All assessments except as noted above for the 24-hour UPCR will be based on the spot UPCR. The change in proteinuria will also be assessed based on spot UPCR at Weeks 24, 52 and 104. The spot UPCR sample should be taken prior to administration of IP, on a clean catch urine sampling. The same urine sample can be used for spot UPCR and sediment analysis.

- Urine sediment examination will be performed at all visits: Selected sites will perform local urinalysis including a microscopic examination. The microscopic examination must be assessed by trained personnel, and can be assessed by the site or a local laboratory. This data will be used for exploratory analyses. This will be in addition to the central laboratory urinalysis.
- Estimated glomerular filtration rate based on the MDRD formula calculated by the central laboratory. Refer to the Laboratory Manual for specifics.

The efficacy assessments based on clinical evaluation include SLEDAI-2K (Section 5.1.2, Appendix F), PGA (Section 5.1.4), OCS reduction (Section 5.1.5), and SDI (Section 5.1.3). The assessments for quality of life and patient-reported outcomes are summarised in Section 5.3.1.

5.1.1 Renal biopsy

Renal biopsy is required within 12 weeks prior to screening or during the screening period for inclusion in the study and must meet inclusion criterion number 6 and not meet exclusion criterion number 10. (Note: If renal biopsy is performed during the screening period, adequate time should be allowed before the next scheduled urine sample collection).

Renal biopsy adjudication

Biopsies will be evaluated locally and the local classification will be used to confirm the eligibility criteria. Screening biopsy slides will then be submitted for adjudication by an external adjudication committee consisting of nephrologists with special expertise in LN. The biopsies will be assessed for all elements of the ISN/RPS classification, the NIH activity, chronicity indices, and the presence of concomitant conditions. The submission of screening biopsies for adjudication is required to participate in the study. The process for adjudication will be defined in a separate document (Renal Biopsy Adjudication Charter). Data obtained during the adjudication will be used for exploratory and sensitivity analyses.

A second renal biopsy is recommended for subjects who meet withdrawal criteria for worsening LN at Week 24 or later and for subjects not achieving CRR at Week 52. This biopsy will be performed at the discretion of the Investigator based on clinical indication and local practice. A separate consent is required for this second biopsy. Second biopsies will be

read locally first and, if the subject agrees, will then be submitted for adjudication to the external adjudication committee. Not agreeing to the review of the second biopsy by the adjudication group will not have any impact on the subject's continuation in the study. If a clinically indicated renal biopsy is performed during the second year extension period, the subject's consent will be required prior to the biopsy slides being submitted for adjudication.

5.1.2 Systemic Lupus Erythematosus Disease Activity Index 2000

The SLEDAI-2K index (see [Appendix F](#)) consists of a list of organ manifestations, each with a definition. A certified Investigator or designated physician will complete the SLEDAI 2K assessment and decide whether each manifestation is "present" or "absent" in the last 30 days. The assessment also includes the collection of whole blood for analysis of C3, and C4 complement levels, and anti-dsDNA antibodies.

The proteinuria descriptor should be scored using the spot UPCR.

The SLEDAI-2K assessment consists of 24 lupus-related items. It is a weighted instrument, in which descriptors are multiplied by a particular organ's "weight". For example, renal descriptors are multiplied by 4 and central nervous descriptors by 8 and these weighted organ manifestations are totalled into the final score. The SLEDAI-2K score range is 0 to 105 points with 0 indicating inactive disease. The SLEDAI-2K scores are valid, reliable, and sensitive clinical assessments of lupus disease activity. The SLEDAI-2K calculated using a timeframe of 30 days prior to a visit for clinical and laboratory values has been shown to be similar to the SLEDAI-2K with a 10-day window ([Touma et al, 2010](#)). A timeframe of 30 days will be used in this study.

Any missing SLEDAI-2K laboratory assessments should be repeated.

5.1.3 Systemic Lupus International Collaborating Clinics/American College Rheumatology damage index

The SDI ([Appendix N](#)) has been developed to assess irreversible damage in SLE subjects independently of its cause (ie, included damage due to SLE activity, SLE-related scarring, therapy, comorbidities) but occurring after disease onset. Damage, ie, irreversible impairment since onset of SLE, is usually defined as a clinical feature that has to be continuously present for at least 6 months to score. In addition some irreversible events such as myocardial infarction or a cerebrovascular accident score as damage on their occurrence. Briefly, damage is defined for 12 organ systems; peripheral vascular, ocular, neuropsychiatric, renal, pulmonary, cardiovascular, gastrointestinal, musculoskeletal, skin, endocrine (diabetes), gonadal, and malignancies. Damage over time can be stable or increase, theoretically to a maximum of 47 points ([Schwartz et al, 2009](#)).

5.1.4 Physician's Global Assessment

A trained and certified Investigator will complete the PGA. The PGA represents the physician's overall assessment of average disease severity on a Visual Analogue Scale (VAS)

scale with 0 (none) to 3 (severe) disease activity over the last 30 days. The PGA for a given subject should be completed by the same physician whenever possible.

PGA may be completed after the visit, to allow for laboratory results to be received, as long as this is done prior to the next scheduled visit. Therefore, the date of the associated scheduled visit (Week 0 etc.) will be used to determine baseline (and subsequent visits), and not the actual date of the assessment.

The PGA is a modification of the classic analogue scale in that it is anchored with numbers from 0 to 3 demarcating mild, moderate and severe disease. The number 3 indicates severe disease and is at the very end of the scale. This refers to the most severe possible disease, and does not reflect the most severe ever seen in a particular subject but the most severe disease ever seen in all SLE subjects. Therefore, the line made by the physician along this scale should virtually never get to this edge. The mark made by the physician must be a single line, nearly perpendicular to the axis of the VAS line and not an “X”. Any disease rated greater than 2.5 is very severe. The range of moderate disease covers about 1.5 to 2.4. Mild disease falls below 1.5. Clearly, this is a bit like a logarithmic scale with greater distances or demarcations possible among more mild-moderate symptoms. This needs to be kept in mind when scoring the instrument.

When scoring the PGA, always look back at the score from the previous protocol visit and move the mark relative to that previous visit. This is a global assessment, factoring in all aspects of the subject’s lupus disease activity. It should not reflect non-lupus medical conditions.

These instructions are quite discrete from those given for other analogue (Likert) scales and are specific for the scoring of the PGA.

5.1.5 Oral corticosteroid reduction

Please refer to Section [7.7.3.2](#) for all information regarding steroid tapering.

5.2 Safety assessments

Key safety assessments are AEs, AESIs, vital signs, physical examination, safety laboratory tests, ECGs, C-SSRS, PHQ-8, and SLEDAI-2K based Flare Assessment Instrument ([Appendix M](#)). Safety assessments will be made at the times indicated in the Study Plan (see [Table 2](#), [Table 3](#), [Table 4](#), and [Table 5](#)).

5.2.1 Adverse events

Adverse events, SAEs, and AESIs are defined in Sections [6.1](#), [6.2](#), and [6.4](#), respectively.

Recording of AEs is described in Section [6.5](#) and reporting of SAEs in Section [6.6](#).

5.2.2 Vital signs

Vital signs (temperature, blood pressure [BP], pulse rate, and respiratory rate) will be obtained at each visit. Specific information on vital signs surrounding the infusion is included in Section 7.2.4 (Subject Monitoring/Procedures During and After Infusions). Temperature should be measured by the same methodology (eg, oral, tympanic) for a subject throughout the study.

5.2.3 Physical examination

Body height will be captured at screening only. Subjects will be weighed at each study visit. Medically significant changes from the Screening physical examination will be recorded as AEs.

5.2.3.1 Complete physical examination

A complete physical examination will be performed at the visits specified in the Study Plan (Table 2, Table 3, Table 4, and Table 5), and will include an assessment of the following: head, eyes, ears, nose and throat, lungs heart, abdomen, joints, muscles and soft tissues, neurologic system, skin, and lymph nodes.

5.2.3.2 Focused physical examination

The focused physical examination will include an assessment of the organ systems required to complete protocol-specified assessment tool (SLEDAI-2K). Additional assessments should be done as clinically indicated. Abnormal findings will be recorded as part of AE, SAE, AESI, or lupus activity, as appropriate.

5.2.3.3 Pap smear

Most cases of cervical cancer appear to be related to infection with human papilloma virus. Because of the potential for viral reactivation due to blockade of the interferon pathway, cervical dysplasia will be assessed in this study, although to date there has been no signal in the anifrolumab studies.

Abnormal Pap smear results received anytime within the 2 years prior to randomisation must be repeated to ensure subject eligibility. If a Pap smear performed within 2 years prior to signing the ICF was normal with no documented malignancy (eg, CIN III, CIS, or AIS), it does not need to be repeated. Subjects with abnormal Pap smear results of atypical squamous cells of undetermined significance (ASC-US), atypical squamous cells where high-grade squamous intraepithelial lesion (HSIL) cannot be ruled out (ASC-H), atypical glandular cells (AGC), or CIN grades I and II (CIN I and II) will be allowed to enter the study; please refer to [Appendix K](#) for guidance.

Female subjects with an intact cervix must have a Pap smear repeated between Week 48 and Week 52 and Week 100 and Week 104 to ensure that there is no evidence of new cervical dysplasia. If a Pap smear was performed between Week 48 and Week 52 and is not normal but

shows no evidence of malignancy (eg, CIN III, CIS, or AIS), it should be repeated as per the subject's gynaecologist's recommendations. If the subject's gynaecologist has recommended a repeat Pap smear be performed at a specified interval, the Pap smear should be obtained as recommended and the report provided in the source document.

5.2.3.4 Assessment of Cushingoid features

Subjects will be assessed for Cushingoid features at the visits specified in the Treatment Period Study Plan (Table 2 and Table 4). Features, such as moon face, buffalo hump, purple or violaceous striae, central obesity, hirsutism, acne, easy bruising, and fragile skin will be captured separately within the study eCRF to evaluate whether resolution of same can occur overtime with OCS reduction.

5.2.4 Electrocardiogram

A 12-lead ECG tracing will be performed locally at the visits specified in the Study Plan (Table 2 and Table 4). The Investigator or qualified designee must review the ECG for clinically significant changes.

5.2.5 Assessment of cardiovascular risk

To understand the contribution of the chronic inflammatory response in SLE to dyslipidaemia (as a potential risk for accelerated subclinical arteriosclerotic cardiovascular disease) and the potential effects of anifrolumab treatment, lipids (including high density lipoprotein cholesterol, low density lipoprotein cholesterol, triglycerides [see Section 5.2.10.1]) will be measured during the study. Current and previous concomitant medications received for cardiovascular indications and other risk factors for cardiovascular disease such as smoking, hypertension, and diabetes should be collected and recorded. Assessment of cardiovascular risk will be completed as indicated in the Study Plan (Table 2 and Table 4).

5.2.6 Columbia-Suicide Severity Rating Scale

The C-SSRS is a unique, simple, and short method of assessing both behaviour and ideation that tracks all suicidal events, and provides a summary of suicidality (Posner et al, 2007). It assesses the lethality of attempts and other features of ideation (frequency, duration, controllability, reasons for ideation, and deterrents), all of which are significantly predictive of completed suicide.

The C-SSRS will be administered by a trained rater. The trained rater will record the clinical observation on the scale, which will be used as the source document. If at all possible, the same individual should perform the assessment at each visit to reduce scoring variability. In the event the primary rater is not available, a designated back-up rater who meets the same qualifications may perform the C-SSRS. If a subject indicates having a rating of type 4 or 5 suicidal ideation on the C-SSRS suicidal ideation scale at any time since the previous visit when the C-SSRS was administered or indicates having had any suicidal behaviour since the previous visit, the subject should be referred to a mental health professional immediately. If

the C-SSRS is administered by a rater other than the Investigator, it is recommended that the Investigator confirms suicidal ideation before making a referral to mental health services; however this should not delay the referral.

5.2.7 Personal Health Questionnaire Depression Scale–8

The PHQ-8 consists of eight of the nine criteria on which the DSM-IV diagnosis of depressive disorders is based ([American Psychiatric Association, 1994](#)). It assesses symptoms of depression over the last 2 weeks. The PHQ-8 is completed by the subject and scored by the investigator at visits specified in the Treatment and Follow-up Study Plans ([Table 2](#) and [Table 3](#)). In addition to the 8 questions on depression, there is also a non-scored question to assess how the depressive symptoms affect the subject's level of functioning.

5.2.8 SLEDAI-2K based Flare Assessment Instrument

SLEDAI-2K based Flare Assessment Instrument is modelled after the modified SELENA SLEDAI Flare Assessment Instrument specifically for this study to collect extra-renal flare data.

Extra-renal flares will be assessed over the previous 30 days for the following components:

- Flare assessment based on total score changes of non-renal components of the SLEDAI-2K
- New/worse SLE manifestations (including items that are not included in the SLEDAI-2K instrument)
- Hospitalisation (including hospitalisations due to LN)
- PGA

Please refer to [Appendix M](#) for details. Flare will be scored in comparison to the previous protocol visit (ie, over the past 30 days) and will only include findings which, in the opinion of the investigator, are due SLE disease activity within that timeframe.

This assessment should be completed by the investigator or delegated/qualified physician. Training and certification of Investigators and designated site personnel who will be completing this assessment will be conducted. The method of training and training documentation is as described in [Section 9.1.1](#) for the efficacy assessments.

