8.5.4 Analysis of safety variables

Adverse events (including AESIs) will be summarised by means of counts summaries by Medical Dictionary for Regulatory Activities (MedDRA) System Organ Class and Preferred Term separately for the study periods (treatment period and follow-up period). All AEs will be listed.

Laboratory data for haematology and clinical chemistry will be summarised. The frequency of changes with respect to normal ranges between baseline and each post-treatment time point will be tabulated. Frequencies of clinically noteworthy values (defined in the SAP) occurring during the clinical study will also be given. Shifts from normal to abnormal between baseline and each post baseline time point will be evaluated for urinalysis.

The incidence of markedly abnormal values and changes from baseline in the ECG parameters will be summarised by treatment group.

The proportion of subjects with suicidal behaviour and suicidal ideation throughout the study based on the C-SSRS will be presented for each treatment group. The proportion of subjects within each of the 4 suicidal behaviour categories and within each of the 5 suicidal ideation sub-categories will also be presented for each treatment group. Descriptive statistics on the total number of attempts, total number of interrupted attempts, and total number of aborted attempts will be summarised for each treatment group.

SLEDAI-2K based Flare Assessment Instrument to capture extra-renal flares: The SLEDAI 2K based Flare Assessment Instrument has 2 sets of definitions: one for severe and one for mild/moderate flares. For the purpose of assessing extra-renal flares the renal components will not be considered for the SLEDAI 2K score. SLEDAI-2K based Flare will be summarised as appropriate.

Other safety variables will be summarised as appropriate. Further details are provided in the SAP.

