3.6.4 SLEDAI-2K-based flare assessment instrument

The SLEDAI-2K based Flare Assessment Instrument will be used to assess the extra-renal flares. Flares will be categorised as mild/moderate or severe and defined as any one criterion

in either the mild/moderate and/or severe flare categories. New or worsened manifestation should only be reported for manifestations of SLE. The distinction between mild and moderate flare will be based on investigators' judgement. The SLEDAI-2K based Flare Assessment Instrument consists of the following parts:

- Mild/moderate flare
 - Change in non-renal components of the SLEDAI-2K
 - New/worse manifestations of SLE
 - PGA
- Severe flare
 - Change in non-renal components of the SLEDAI-2K
 - New/worse manifestations of SLE
 - Hospitalisation
 - PGA

See Appendix M in the clinical study protocol for further details. Flares will be scored in comparison to the previous study visit (i.e. over the past 30 days) and will only include findings which, in the opinion of the investigator, are due to SLE disease activity within that timeframe.

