4.2.6.4 SLEDAI-2K-based flare assessment instrument

The flare rate per of subject years for extra-renal flares will be presented overall, and by timing ("on-treatment" and "off-treatment"), for mild/moderate flares, severe flares and any flares, respectively. An "on-treatment" flare is defined as a flare with a date of onset after the date of first dose of IP and on or prior to the date of last dose of IP + 28 days. An "off-treatment" flare is defined as a flare with a date of onset after the date of last dose of IP + 28 days. Where a flare has been marked as both mild/moderate and severe, it will be considered to be severe for the purposes of this summary.

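### The extra-renal flare rate counts an admission for lupus nephritis alone as a severe extra-renal flare

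*Protocol*

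**What the plan says.** Extra-renal flares, measured with the SLEDAI-2K based Flare Assessment Instrument, are a named outcome of the safety objective (Protocol 2.3, SAP 1.1.3). Protocol 5.2.8 says the instrument was adapted "specifically for this study to collect extra-renal flare data" and introduces its content with "Extra-renal flares will be assessed over the previous 30 days for the following components". Four components follow:

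- change in the non-renal SLEDAI-2K score;
- new or worse SLE manifestations;
- "Hospitalisation (including hospitalisations due to LN" (the parenthesis closes there);
- PGA.

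The section adds that scoring "will only include findings which, in the opinion of the investigator, are due SLE disease activity within that timeframe" and refers to Appendix M for details.

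Protocol 8.5.4 gives the renal exclusion: "For the purpose of assessing extra-renal flares the renal components will not be considered for the SLEDAI 2K score". SAP 3.6.4 gives the combination rule, "Flares will be categorised as mild/moderate or severe and defined as any one criterion" in the relevant category. It lists PGA under both severities and hospitalisation under severe only. SAP 4.2.6.4 gives the output: "The flare rate per of subject years for extra-renal flares will be presented overall", with splits by on- and off-treatment timing and by severity. A flare marked as both severities is treated as severe.

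**The concern.** The sponsor wanted an extra-renal measure and took the renal items out of the SLEDAI-2K score to get one. The hospitalisation component then lets renal disease back in by name.

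Everyone enrolled has active proliferative LN, and the treatment is meant to change renal outcome. If the arms differ in LN admissions, that difference enters the extra-renal severe flare rate. A renal benefit could then look like fewer extra-renal flares, and renal failure of therapy could look like an extra-renal safety signal. Renal flares are summarised separately (Protocol 8.5.3), so one renal event may appear under both headings.

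The timing split may add to the problem. Worsening LN is itself a reason to stop investigational product (Protocol 3.9.1). An LN admission more than 28 days after the last dose would fall in the off-treatment extra-renal rate.

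**Working it through.** The plan states no figure on this point, so the check is a trace through the definitions.

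**Case 1: admission for LN only.** Take a subject admitted for LN, with no change in non-renal SLEDAI-2K and no new or worse non-renal manifestation.

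1. Is the hospitalisation component met? Yes. Protocol 5.2.8 names LN admissions as included.
2. Does the attribution filter remove it? No. The filter asks whether the finding is due to SLE activity, and LN is SLE activity.
3. Does the renal exclusion remove it? No. In Protocol 5.2.8, Protocol 8.5.4 and SAP 3.6.4 that exclusion applies to the SLEDAI-2K score and not to hospitalisation.
4. Is one criterion enough, and at what severity? Yes, under SAP 3.6.4, and hospitalisation sits under severe.
5. Does the analysis remove it? No. SAP 4.2.6.4 contains no such rule.

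Result: one severe extra-renal flare.

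**Case 2: renal worsening without admission.**

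1. Does the PGA reflect the kidney? Yes. Protocol 5.1.4 says "This is a global assessment, factoring in all aspects of the" subject's lupus activity and leaves out only non-lupus conditions. Protocol 6.5.7 says that worsening of LN is recorded in the PGA, among other tools.
2. Does the rise meet the instrument's PGA criterion? This cannot be determined. The cut-offs, and any renal instruction attached to the item, are in Appendix M.

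Result: possible, not established.

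**Size.** Let E be the rate of severe flares that meet some other criterion, and L the rate of severe flares met solely by LN hospitalisation, both per subject-year. The reported severe rate is E + L, and the inflation factor is (E + L)/E = 1 + L/E. For anifrolumab minus placebo, the reported difference is (E_A − E_P) + (L_A − L_P). The second bracket is purely renal and vanishes only if LN-only admissions are equally frequent in both groups. The documents give no value for E or L, so no factor can be computed.

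**The case against.** The inclusion of LN admissions is an explicit parenthesis in an instrument modelled on an existing one, so it looks deliberate. That is fair, but intent does not settle the label. Counting LN admissions suits an all-SLE flare measure and does not suit a rate titled extra-renal.

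The consequences are also limited, and this part of the objection stands. The outcome is descriptive and lies outside the testing hierarchy (Protocol 8.6, SAP 4.1.2). Extra-renal activity is measured without renal items through change in non-renal SLEDAI-2K (Protocol 8.4.3.13, SAP 3.3.15 and 4.2.3.11). Disease worsening that leads to hospitalisation is reported as a serious adverse event (Protocol 6.2 and 6.5.7), so a careful reader could cross-check a difference in severe flares.

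A reader might infer more than the documents support:

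- *Any renal worsening becomes an extra-renal flare.* Through these two components it does so only if it leads to admission or to a qualifying PGA rise.
- *A PGA rise caused by proteinuria alone makes a severe flare.* This cannot be verified without Appendix M, and an appendix missing from the supplied text is not a fault of the plan.
- *The extra-renal safety question cannot be answered.* At most this holds for this one rate, given the separate non-renal SLEDAI-2K analysis.
- *The rate is inflated by some stated multiple.* Any multiple would only return the values assumed for E and L. It would also shrink where LN admissions coincide with flares already counted through another criterion.
- *Every flare met only by PGA should be removed.* The PGA also captures genuine extra-renal worsening, so removal would replace over-counting with under-counting.

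**Conclusion.** The concern holds for hospitalisation. As written, an admission for LN alone is counted as a severe extra-renal flare, and nothing in the supplied text removes it. For PGA it is conditional on the criteria in Appendix M.

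The effect is on interpretation of one descriptive safety rate; type I error and power are untouched. The size is unknown and depends on how often LN-only admissions occur and whether they differ between arms. The conclusion assumes that Appendix M does not override the LN inclusion stated in Protocol 5.2.8. It is worth correcting because the rate does not measure what its name says and the correction is cheap.

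**What to change.** In SAP 4.2.6.4, before unblinding:

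1. Exclude from the extra-renal rate any flare met solely by hospitalisation due to LN, and show those flares in a separate row.
2. Keep an all-flare row, so that nothing is lost.
3. As a sensitivity row, show the extra-renal rate with and without flares met solely by PGA. Do not remove them outright.
4. Align Protocol 5.2.8 and SAP 3.6.4 with this definition, and check Appendix M against it.

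The cost is SAP wording, one derivation and a blinded classification of the cause of each SLE admission. The source data should exist: admissions meeting seriousness criteria are reported with hospitalisation dates (Protocol 6.5.3 and 6.5.7), and a medical review team that stays blinded already reviews the flare instrument alongside adverse event data (Protocol 9.2.4). The derivation also needs the flare dataset to hold which component was met. The supplied text does not confirm this, so it should be checked first.
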